1.1 STUDY DESIGN

This was a prospective cohort study.

1.2 STUDY SETTING

This was a single center, hospital based study done in Mulago National Referral Hospital. Mulago National Referral Hospital is the Makerere University teaching hospital and is located in Kampala. It has a 1500 bed capacity but can admit up to 2500 patients.

This study was carried out in various theatres of Mulago hospital from August 2018 to January 2019. The theatres that were used for this study were: the main operating theatre, obstetrics and gynecology theatres, the orthopedics and ophthalmology theatres. These were a total of eight operating tables with an average of fifteen surgeries daily.

1.3 STUDY POPULATION

The target population was all patients 18 years of age and above scheduled for an elective or emergency surgical procedure under regional anaesthesia at Mulago hospital. The accessible population included all patients attending Mulago hospital for elective and emergency surgery under regional anaesthesia during the study period from August 2018 to January 2019.

1.4 ELIGIBILITY CRITERIA

1.4.1 INCLUSION CRITERIA

Patients having emergency or elective surgery under regional anaesthesia.

Patients aged 18 years and above.

ASA class 1, 2, 3 and 4 patients

Patients who consented to being a part of the study.

1.4.2 EXCLUSION CRITERIA

Patients who were switched to general anaesthesia after planned regional anaesthesia.

Patients with nausea and vomiting from pre-existing co-morbidities.

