1.8 DATA MANAGEMENT

1.8.1 DATA COLLECTION

A standardised questionnaire was completed by the study research assistants or the principal investigator during the immediate pre-operative period to assess pre-operative risk of post-operative nausea and vomiting. The information collected included patient demographics, past medical history, information on fasting and co-morbidities. A second questionnaire was used to assess the perioperative conduct of anaesthesia and any events occurring within this period. It contained the follow up information as well.

Patients were followed up once at 24 hours to assess for post-operative nausea and vomiting.

1.8.2 INDEPENDENT VARIABLES:

Socio demographic data such as age and sex, the diagnosis and type of procedure, ASA classification, history of PONV or motion sickness, non-smokers, peri-operative opioid use, period of pre-operative fasting, PONV prophylaxis use, duration of anaesthesia and surgery were studied.

1.8.3 DEPENDENT VARIABLE:

Post-operative nausea and vomiting measured by any retching, nausea or vomiting within 24 hours following surgery under regional anaesthesia.

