1.8.4 DATA ANALYSIS AND SAFETY

Completeness and accuracy of data was checked daily and organised by the principal investigator before storage. Data was double entered into the computer using EPI data version 3.1, and then subsequently exported to STATA version 14.0 for analysis.

Analysis was done using STATA with the help of a statistician. Both raw data and the analysed form were kept both electronically and hardcopy for further reference.

All questionnaires were stored in a secure, waterproof place to enable confidentiality and were only available to the principal investigator.

Participant characteristics were expressed as categorical and/or continuous variables.

Continuous variables were expressed as means and standard deviations while categorical data was expressed as frequencies with their respective proportions. Data presentation is in tabular and graphic forms.

Cumulative incidence was assessed as the proportion of study participants who developed PONV within 24 hours of follow up divided by the total number of study participants enrolled into the study with complete follow up.

At the bivariate level, each variable was compared with the outcome variable using cross tabulation and the logistic analysis. Variables that had p-value less than 0.200 at bivariate analysis were considered for multivariate analysis using logistic regression and variables were considered significant if the p-value <0.05.

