4.1 Have you had nausea or vomiting before?		
1=Yes		

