5.1 Did any of the following happen during recovery? (Tick appropriately)

	1=Yes	2=No
D . 11		
Retching		
Nausea		
rvausca		
Vomiting		

5. At 24 hours (tick)

5.1 Nausea or vomiting 1= Yes 2=No 5.2 If yes, time to occurrence of PONV from time of surgery.....hours.....min

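### Nausea already present before the block is neither clearly excluded nor visibly recorded, so it can be counted as incident PONV

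*Protocol*

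**What the plan says.** Protocol 1.4.2 lists two exclusions. One is a switch to general anaesthesia; the other is "Patients with nausea and vomiting from pre-existing co-morbidities". Section 1.4.1 admits "Patients having emergency or elective surgery under regional anaesthesia", and section 1.2 names the sites as "the main operating theatre, obstetrics and gynecology theatres, the orthopedics and ophthalmology theatres".

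The outcome in 1.8.3 is "Post-operative nausea and vomiting measured by any retching, nausea or vomiting within 24 hours following surgery under regional anaesthesia". Section 1.8.4 calls the result a cumulative incidence: participants who developed PONV, "divided by the total number of study participants enrolled into the study with complete follow up".

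The pre-operative content is summarised in 1.8.1: "The information collected included patient demographics, past medical history, information on fasting and co-morbidities". On the form itself, the nearest pre-operative symptom question is "4.1 Have you had nausea or vomiting before", followed by a rating of how that experience felt. Questionnaire 2 records retching, nausea and vomiting during surgery (item 3.5) and in recovery, and at 24 hours asks "5.1 Nausea or vomiting 1= Yes 2=No" with time to occurrence.

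**The concern.** A cumulative incidence describes new events among people free of the condition when follow-up starts. Here nothing in the eligibility rules, the outcome definition or the denominator requires that. A patient who is vomiting on arrival because of labour or an acute surgical problem can be enrolled as written. If the symptom continues after surgery, the patient enters the numerator.

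For objective 1 this moves the estimate upward whenever patients symptomatic at baseline are more often positive afterwards than the rest. For objective 2 the effect could differ between groups. Obstetric patients are all women, and sex is the factor on which 1.5 sizes objective 2. Type of procedure is a listed independent variable, and urgency is recorded on both questionnaires. If baseline nausea is commoner in some of these groups, part of an apparent association would reflect how patients arrived rather than what happened after anaesthesia.

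**Working it through.** **1. Can the plan, followed as written, count a persisting symptom?**

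- Entry: 1.4.2 excludes by cause. Labour, pregnancy, the presenting surgical condition and pre-operative drugs are not clearly co-morbidities, and the term is not defined.
- Scope: emergency surgery and obstetric theatres are included, and sampling is consecutive (1.6).
- Numerator: any symptom within 24 hours, with no new-onset condition (1.8.3).
- Denominator: everyone with complete follow-up, not only those symptom-free at baseline (1.8.4).
- Record: item 4.1 has no time frame and reads as history. The first symptom checks tied to a defined period are during surgery and in recovery, after the baseline has passed.

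So the answer is yes, and the visible form gives no means of identifying such participants afterwards.

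**2. The plan's own figure.** Inputs from 1.5: Z = 1.96, P = 0.314, D = 0.05.

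N = 1.96² × 0.314 × 0.686 / 0.05² = 330.998, rounded to 331; 331 × 1.10 = 364.1, given as 364. Both reproduce. The 5-point error is the yardstick for what follows.

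**3. Size of the bias for objective 1.** Let s be the share symptomatic at baseline and c the chance that such a participant is recorded as PONV. Take 0.314 as the incidence in the rest.

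Observed = (1 − s) × 0.314 + s × c, so bias = s × (c − 0.314).

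The values of s and c are assumptions; the documents give neither.

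| s | c = 0.50 | c = 0.80 |
|---|---|---|
| 5% | 0.05 × 0.186 = +0.9 points | 0.05 × 0.486 = +2.4 points |
| 10% | 0.10 × 0.186 = +1.9 points | 0.10 × 0.486 = +4.9 points |

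The bias reaches 5 points at s = 0.05 / 0.486 = 10.3% when c = 0.80, and at s = 0.05 / 0.186 = 26.9% when c = 0.50.

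**4. Illustration for objective 2.** Section 1.5 uses 0.065 in men and 0.174 in women, a difference of 10.9 points. Suppose 5% of women and no men are symptomatic at baseline, with c = 0.80 (again assumed). The female proportion becomes 0.174 + 0.05 × (0.80 − 0.174) = 0.205, and the difference 0.205 − 0.065 = 14.0 points. This shows the mechanism only; nothing in the documents supports that particular imbalance.

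**The case against.** The strongest reply is that 1.4.2 does address pre-existing nausea, and that a screener could read co-morbidities broadly enough to include labour or the presenting condition. That is possible, and it would shrink the problem. It does not remove it: the text does not require the broad reading, and no visible item would document that it was applied.

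Second, the available copy of the questionnaire is damaged. Section 1.8.1 says co-morbidities were collected, yet no such item is visible, so an item on current symptoms might also have been lost. This stands as a caveat. The firm statement is that no visible item records baseline symptoms and that the content list in 1.8.1 names none.

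Third, diagnosis, procedure, urgency, intraoperative symptoms and time to occurrence are recorded. They permit useful subgroup and sensitivity analyses, but none is a baseline symptom status. Symptoms during surgery, for example, may be new.

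Fourth, a reader might infer that urgency, procedure and sex are biased as risk factors. The documents do not show that residual baseline nausea concentrates in emergency or obstetric patients, so distortion is plausible rather than established. A reader might also want baseline nausea in the objective 2 model as a routine covariate. That is debatable, because it may lie on the pathway from pregnancy or emergency presentation to PONV, and adjusting could remove part of a real association.

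**Conclusion.** The point holds as a gap in baseline definition and measurement. As written, the plan can count nausea present before the block as incident PONV, and the visible form cannot separate it out. The direction for objective 1 is upward, provided symptomatic arrivals are positive afterwards more often than 31.4%. The size is about +0.9 to +4.9 points for baseline shares of 5–10% and persistence of 50–80%, all assumed, so it could be negligible or nearly as large as the planned error.

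It would go too far to conclude that prevalent cases were in fact enrolled in number, or that the reported incidence is inflated by a known amount. The documents give no rate of pre-operative nausea, and the share that matters is only what remains after the existing exclusion. For objective 2 the conclusion is limited to possible distortion.

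**What to change.** - **Questionnaire 1:** add one yes/no row for nausea, retching or vomiting present immediately before the block. A look-back over the preceding day would be too wide, since it would set aside patients whose symptoms had already resolved.
- **Section 1.8.4, objective 1:** report cumulative incidence among those answering No as the main estimate, with the all-participant figure beside it.
- **Section 1.8.4, objective 2:** repeat the model in the No group as a sensitivity analysis, without making the item a routine covariate.

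The protocol is written in the past tense, with collection from August 2018 to January 2019, so the new row may no longer be possible. In that case, state the limitation and use data already collected: report incidence by urgency, by obstetric versus other procedure, and with participants symptomatic during surgery (item 3.5) set aside. The last is a rough check, because it also removes new intraoperative symptoms.

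The cost is one tick at an existing interview and a short addition to 1.8.4. The main estimate uses slightly fewer participants. If 331 complete follow-up and 10% answer Yes, 331 × 0.90 ≈ 298 remain, and the half-width becomes 1.96 × √(0.314 × 0.686 / 298) = 5.3 points instead of 5.0.

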1.5 SAMPLE SIZE CALCULATION

Objective 1

Assuming an incidence of PONV in regional anaesthesia of 31.4%(Quinn et al., 1994) with an absolute error of 0.05 and 95% CI

Using Kish Leslie formula:

$$N = Z^2 P (1-P)$$

 D^2

Where N=sample size required to determine incidence

Z is the value corresponding to 95% confidence interval=1.96

P is the prevalence of PONV among patients undergoing surgery under regional anaesthesia=0.314 from previous studies

D is the absolute error=0.05

$$N = 1.96 \times 1.96 \times 0.314 (1 - 0.314)$$

 0.05×0.05

N = 331 patients

Adjusting for loss to follow up of 10%

$$N = n (100+10)/100$$

=331(100+10)/100

=364 patients

Objective 2

From the comparison of two proportions formula:

$$N = \frac{\left(Z\alpha\sqrt{\left(\frac{1}{q1} + \frac{1}{q2}\right)P(1-P)} + Z\beta\sqrt{P1(1-P1)\frac{1}{q1} + P2(1-P2)\frac{1}{q2}}\right)^2}{(P1-P2)^2}$$

Using the factor of gender for PONV in regional anaesthesia according to a study by AC Quinn et al 1994

q1 is proportion of males in study =336/606=0.554

q2 is proportion of females in study =270/606=0.446

p1 is proportion of males with PONV =22/336 =0.065

p2 is proportion of females with PONV =47/270 = 0.174

 $P=p1q1+p2q2=(0.065x0.554+0.174x0.446)=0.03601+0.0776=0.1136\sim0.114$

 $Z\alpha$ is standard normal corresponding to level of significance. Using a level of significance of 5%, $Z\alpha$ = 1.96

 $Z\beta$ corresponds to power of the study. For a power of 80% $Z\beta$ = 0.841

N=272patients

Therefore, choosing the larger sample size from the calculation for sample size for the first objective; the sample size used was 364 participants

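### Section 1.5 plans on two irreconcilable PONV incidences, 31.4% and 11.4%, both credited to one 1994 study; at 11.4% the stated reason for N = 364 no longer holds

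*Protocol*

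**What the plan says.** All the planning figures are in protocol section 1.5.

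- **Objective 1** (estimating incidence) begins "Assuming an incidence of PONV in regional anaesthesia of 31.4"%, with a 1994 study as the source. The input is repeated as "P is the prevalence of PONV among patients undergoing surgery under regional anaesthesia=0.314 from previous studies". The precision target is given as "D is the absolute error=0.05". The result is 331, raised by 10% for loss to follow-up to 364.
- **Objective 2** (associated factors, with sex as the example) is introduced by "Using the factor of gender for PONV in regional anaesthesia according to a study by", followed by the same 1994 citation. Its inputs are "p1 is proportion of males with PONV =22/336 =0.065" and "p2 is proportion of females with PONV =47/270 = 0.174", with sex shares 336/606 = 0.554 and 270/606 = 0.446. The protocol pools these to an overall P of 0.1136, rounded to 0.114, and states N = 272 for 80% power at the 5% level.
- **Choice of N:** "choosing the larger sample size from the calculation for sample size for the first objective; the sample size used was 364 participants".

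Section 1.8.3 defines one outcome for the study: "Post-operative nausea and vomiting measured by any retching, nausea or vomiting within 24 hours following surgery under regional anaesthesia".

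**The concern.** The two calculations describe the same quantity, PONV under regional anaesthesia, and cite the same study, yet they assume overall incidences that differ by a factor of almost three (0.314/0.114 = 2.75). An overall rate is a weighted average of the male and female rates, so it must lie between 6.5% and 17.4%. A rate of 31.4% is outside that range. Section 1.5 offers no explanation.

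What is at stake is the justification of the sample size. The planned precision and the claim that objective 1 is the more demanding depend on 0.314. The 80% power for the sex comparison depends on rates that pool to 0.114. Unless an unstated difference in endpoint or patients separates the two figures, at least one of these statements has lost its basis.

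**Working it through.** **Inputs (all from section 1.5).** P = 0.314; D = 0.05; Z = 1.96; 10% loss applied as n × 1.10; q1 = 0.554, q2 = 0.446; p1 = 0.065, p2 = 0.174; Zα = 1.96, Zβ = 0.841.

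**1. Reproducing the plan's figures.**

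- Objective 1: N = Z²P(1−P)/D² = 3.8416 × 0.314 × 0.686 / 0.0025 = 331.0, and 331 × 1.10 = 364.1. Both stated figures reproduce.
- Objective 2, by the protocol's formula with P = 0.1136: the first square root is 0.6384 and the second 0.6572, so N = (1.96 × 0.6384 + 0.841 × 0.6572)² / 0.109² = 273.9. With P rounded to 0.114 it is 274.5. The stated 272 is within about 1%, and the difference does not matter here.

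Each formula is therefore applied correctly to its own inputs. The conflict is between the inputs.

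**2. The two incidences.** From the protocol's counts, (22 + 47)/606 = 69/606 = 0.1139. An incidence of 31.4% among 606 patients would be about 190 cases (0.314 × 606 = 190.3), not 69. With the stated sex shares and an overall 0.314:

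- keeping men at 6.5% requires women at (0.314 − 0.065 × 0.554)/0.446 = 62.3%;
- keeping women at 17.4% requires men at (0.314 − 0.174 × 0.446)/0.554 = 42.7%.

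**3. If 0.114 is right.**

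- Objective 1: 3.8416 × 0.114 × 0.886 / 0.0025 = 155.2, so 156; with loss 156 × 1.10 = 171.6, about 172.
- Objective 2: 272 as stated; with loss 272 × 1.10 = 299.2.
- The order reverses. Before inflation, objective 1 exceeds 272 only for P between about 0.23 and 0.77. Comparing its inflated N with the uninflated 272, as the protocol does, widens this to about 0.20 to 0.80. At 0.114 objective 2 is larger on either comparison.
- With 331 completers, the 95% half-width is 1.96 × √(0.114 × 0.886/331) = 0.034, and power for the sex comparison is about 87%.

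**4. If 0.314 is right.** Objective 1 is unchanged. Objective 2 needs new sex-specific rates that average to 0.314. The protocol gives none, so the contrasts below are assumptions that show the range:

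| Feature carried over from 6.5% v 17.4% | Men | Women | N for 80% power |
|---|---|---|---|
| Risk ratio 2.68 | 0.180 | 0.481 | 75 |
| Odds ratio 3.03 | 0.209 | 0.445 | 123 |
| Difference 10.9 points | 0.265 | 0.374 | 577 |

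In the last case, 331 completers give about 56% power. With 331 completers, 80% power requires a difference of about 14.4 points (0.250 v 0.394).

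**The case against.** The strongest reply is that the 1994 study cannot be seen from here. It may report nausea and vomiting separately, or by subset, so that both figures are correct for different things. Section 1.8.3 fixes this study's outcome, not what the cited study counted, and the definition of P speaks of previous studies in the plural. This stands to the extent that nobody can say from the protocol which figure is wrong. It does not remove the problem: the opening line of objective 1 names the 1994 study as the source of 31.4%, both figures carry the same description, and both are used to plan for the study's single outcome. If an explanation exists, section 1.5 has to give it.

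A second reply is that little harm follows. At 0.114 the sample is more than adequate for both objectives. At 0.314 a required N anywhere from 75 to 577 demonstrates no shortfall. The protocol is written in the past tense, with data collection from August 2018 to January 2019, and the incidence estimate itself will not depend on the planning value. All of this is fair, and it limits the weight of the point: what fails is the stated basis for the sample size, and the sample is not shown to be too small.

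**Conclusion.** The concern holds. As written, section 1.5 attributes two overall PONV incidences to one source, and its own sex-specific rates rule out 31.4%.

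If 0.114 is right, objective 1 needs 156 rather than 331, neither calculation yields 364, and the closing sentence names the wrong objective as decisive. The expected half-width is then 3.4 points, not 5, and power for the sex comparison is about 87% with 331 completers. If 0.314 is right, objective 1 stands, but p1 and p2 cannot both be correct and the 80% power is unsupported, without being shown to be too low.

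These conclusions assume that both figures refer to the same endpoint in comparable patients, as the wording of section 1.5 implies. The sample sizes in the 0.314 case also rest on the assumed contrasts. This should be fixed, because section 1.6 makes the resulting number the point at which recruitment stops.

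**What to change.** Check the 1994 source. Then use one overall incidence in both calculations, or state the endpoint, subset or time window that makes the two figures differ and say which applies to the outcome in section 1.8.3.

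- **If it is 0.114:** restate objective 1 as N = 156 for ±5 points, or as ±3.4 points with 331 completers. Correct the sentence on which objective gives the larger N, and state that 364 exceeds both requirements.
- **If it is 0.314:** replace p1 and p2 with sex-specific rates that average to 0.314, give their source, and restate the power for objective 2 at 331 completers, whatever it turns out to be.

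The cost is one source check and some recalculation and rewording within section 1.5. The correction restates figures and does not itself call for more enrolment. The one drawback is that the restated power for objective 2 may be less favourable than 80%.

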1.6 SAMPLING METHOD

Consecutive sampling was used until the sample size was attained.

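### The 10% loss allowance is added to the 331 completers (364) rather than taken from those enrolled (368), so 364 covers only 9.1% loss; the effect on precision is small

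*Protocol*

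**What the plan says.** Section 1.5, Objective 1, sizes the study for a single proportion and arrives at "N = 331 patients". Under the line "Adjusting for loss to follow up of 10" per cent, it multiplies that number by (100+10)/100 and obtains 364. Objective 2 gives a smaller figure, 272, so the section closes on the Objective 1 result: "the sample size used was 364 participants".

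Two other places bear on the point. Section 1.6 gives the stopping rule for enrolment: "Consecutive sampling was used until the sample size was attained". Section 1.8.4 takes as denominator of the cumulative incidence the "total number of study participants enrolled into the study with complete follow up".

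**The concern.** An allowance for loss has one job: after the assumed loss, the number still evaluable should be at least the number the precision formula asked for. Loss to follow-up is a fraction of the people enrolled, so the required number has to be divided by one minus that fraction. Multiplying by one plus the fraction takes the 10% from the smaller, post-loss number and always gives too few.

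This bears on the estimate because section 1.8.4 drops incompletely followed patients from the denominator. The ±5-point target therefore depends on completers, not on enrolment. At stake is whether 364 meets the two inputs it is said to meet together: 10% loss, and an absolute error of 0.05 at an incidence of 0.314.

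**Working it through.** **Inputs, all from section 1.5**
- Incidence: "P is the prevalence of PONV among patients undergoing surgery under regional anaesthesia=0.314 from previous studies"
- Confidence: "Z is the value corresponding to 95% confidence interval=1.96"
- Precision: "D is the absolute error=0.05"
- Loss to follow-up: 10%

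**1. Reproduce the protocol's figures**
- N = Z²P(1−P)/D² = 1.96² × 0.314 × 0.686 / 0.05² = 330.998, so 331. Reproduced.
- 331 × 1.10 = 364.1, given as 364. Reproduced.

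**2. Test 364 against the stated loss**
- 10% of 364 is 36.4 lost, leaving 364 − 36.4 = 327.6 completers, below 331.
- Patients that can be lost while keeping 331: 364 − 331 = 33, and 33/364 = 9.07%.

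**3. Enrolment that does meet the stated loss**
- N × 0.90 ≥ 331 gives N ≥ 331/0.90 = 367.8, so 368.
- Check: 368 × 0.90 = 331.2.
- Difference from the protocol: 368 − 364 = 4 patients, 4/364 = 1.1%.

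**4. Effect on precision**

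Half-width = 1.96 × √(0.314 × 0.686 / n):

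| Completers n | Half-width (percentage points) |
|---|---|
| 331 | 5.00 |
| 328 | 5.02 |
| 327.6 | 5.03 |
| 327 | 5.03 |

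**5. When the shortfall decides anything**
- With 327.6 completers, ±5 points holds while P(1−P) ≤ 327.6 × 0.05²/1.96² = 0.2132, that is for an incidence up to about 30.8%.
- With 331 completers the corresponding limit is 31.4%, the planning value itself.
- At 10% loss, the missing patients decide whether ±5 is met only for an incidence between about 30.8% and 31.4%.

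**6. Objective 2 does not change the result**
- Its stated 272, divided by 0.90, is 302.2, still below 364. Objective 1 drives the sample size either way.

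**The case against.** The strongest reply is that nothing was miscalculated. The protocol prints its rule and evaluates it correctly, and it never says that the 10% is a share of those enrolled. That is fair as a description: the fault lies in the choice of base, not in the multiplication. It does not rescue the figure, because the line is presented as an adjustment for 10% loss to follow-up, and a study of 364 that loses 10% of its patients does not keep 331.

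The second reply is materiality, and it stands. A half-width of 0.0502 to 0.0503 rounds to the stated 0.05. Follow-up is a single contact at 24 hours after hospital surgery, and the document gives no reason to expect loss above 9%. No analysis or conclusion turns on four patients.

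Third, the value of P is itself uncertain. The Objective 2 counts, attributed to the same cited study, give (22+47)/606 = 0.114. At that incidence the same formula needs only about 155 patients, and 327 completers would give about ±3.4 points. The documents alone cannot settle which value is right. This limits the practical weight of the point but does not make the allowance correct at the P that the protocol chose.

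Fourth, the document is written in the past tense and reports 364 as the size used, so changing the line to 368 would set the calculation against what was done. That stands, and it governs the choice of fix.

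One could also read 364 as a count of completers, in which case no precision is lost. But the section builds 364 as 331 plus a loss allowance, which makes it an enrolment figure, and no replacement of lost patients is described.

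**Conclusion.** The point holds, and it is minor. As written, 364 does not cover a 10% loss; it covers 9.07%. The number consistent with the protocol's own inputs is 368, a gap of 4 patients (1.1%). At a full 10% loss the half-width is 5.02 to 5.03 points instead of 5.00, which does not materially weaken the incidence estimate. If 33 or fewer patients were lost, there is no shortfall.

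This rests on three assumptions:
- P = 0.314 is taken as stated.
- The 10% is read as a share of those enrolled.
- 364 is the number enrolled, with lost patients not replaced.

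No figure is put on patients switched to general anaesthesia, whom section 1.4.2 excludes. They would lower the evaluable number further only if they count towards 364 and are not replaced, which the protocol leaves open.

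**What to change.** Keep 364, since it is reported as the size used, and amend the inflation line in section 1.5. It should say that 364 allows for a loss of 9.1% while retaining 331 completers, and that at 10% loss about 327 to 328 would remain, giving about ±5.03 points at an incidence of 31.4%.

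If the section is meant only to record the planning calculation, the line can instead read 331/0.90 = 368, with a note that 364 were used. Keeping 364 is preferable because it agrees with what was done.

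The cost is one restated line. No further patients are needed, and the data and the analysis stay as they are.
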